2.1 Investigational product(s)

BCM-95® curcumin 3 gram per day

2.2 Animal and preclinical study data

Guo et al: curcumin can promote Bax, TP53 gene, activated the caspase-3 and caspase-9 in CRC cell line (LoVo), which can induce cancer cell apoptosis. [15]

Mosieniak et al.: curcumin can activate senescence and autophagy via p53 and p21 overexpression. [16]

NF- κ B Ionizing radiation (IR) is well recognized for activating the transcription factor NF- κ B, a key mediator of both cancer cell resistance to treatment and radiation-induced normal tissue toxicity [17]. In cancer cells, NF- κ B drives the activation of pro-survival signaling pathways, facilitating tumor growth and progression. Additionally, NF- κ B regulates the expression of numerous cytokines and chemokines with strong pro-inflammatory properties, which can exacerbate tissue injury following IR exposure [18].

Curcumin has been shown to inhibit the proliferation and post-irradiation clonogenic survival of multiple colorectal cancer cell lines. While ionizing radiation activates NF- κ B in a dose- and time-dependent fashion, curcumin effectively counteracts this by preventing the phosphorylation and degradation of I κ B α , inhibiting I κ B kinase activity, and reducing Akt phosphorylation. It also suppresses the expression of key NF- κ B-regulated proteins, including Bcl-2, Bcl-xL, IAP-2, COX-2, and cyclin D1, thereby enhancing the therapeutic efficacy of radiotherapy [19].

In addition to its radiosensitizing effects, curcumin also demonstrated protective activity in normal intestinal cells exposed to Irinotecan. It blocked NF-κB signaling and mitigated Irinotecan-induced apoptosis by upregulating molecular chaperones such as GRP78, P4HB, and PRDX4, while downregulating pro-apoptotic proteins like CHOP and cleaved caspase-3. These protective effects are mediated through curcumin's inhibition of NF-κB activation, along with its ability to reduce oxidative stress and endoplasmic reticulum stress, ultimately alleviating intestinal mucosal injury caused by chemotherapy [11].

2.3 Clinical data

Howells et al.: Curcumin is a safe and tolerable adjunct to FOLFOX chemotherapy in metastatic colorectal cancer patients with potential benefits of overall survival. [20]

Carroll et al: Curcumin 4g per day can reduce 40% of aberrant crypt foci in the rectum of healthy smokers [21]

2.4 Risks / benefits Assessment

Benefit: the anti-inflammation and anti-neoplastic effect of curcumin may alleviate the side effect or improved the tumor response to neoadjuvant chemotherapy and radiation therapy.

Risk: the limited case reports of curcumin on hepatitis and iron metabolism may effect patient with relative underlying disease such as active hepatitis or iron metabolic diseases.[1, 22]

2.5 Regulatory

This study will be conducted in compliance with the protocol approved by the Institutional Review Board, and according to Good Clinical Practice standards. No deviation from the protocol will be implemented without the prior review and approval of the IRB except where it may be necessary to eliminate an immediate hazard to a research subject. In such case, the deviation will be reported to the IRB as soon as possible.

3. Objectives and Endpoints

3.1 Study Objectives:

3.1.1 *Primary objective*: the anti-inflammation effect of curcumin on the radiation proctitis, adverse events and completion of neoadjuvant radiation therapy and chemotherapy

3.1.2 *Secondary objectives*: the anti-neoplastic effect of curcumin on the treatment of rectal cancer in adjuvant with radiation therapy and chemotherapy

3.2 Study endpoints:

3.2.1 *Primary endpoint*:

1. **Grade 3 enteritis/proctitis**: evaluated by National Cancer Institute Common Terminology Criteria for Adverse Events Version 5.0 (NCI CTCAE v. 5.0) and colonoscopy evaluation 2 weeks after radiation therapy completed

3.2.2 *Secondary endpoints*:

1. Any grade III adverse events during the neoadjuvant therapy: evaluated by National Cancer Institute Common Terminology Criteria for Adverse Events Version 5.0 (NCI CTCAE v. 5.0)

2. Clinical complete response rate of the primary tumor after completion of the neoadjuvant treatment: evaluated by Response Evaluation Criteria in Solid Tumors Version 1.1 (RECIST v1.1)
3. Pathological or clinical complete response rate of the primary tumor after completion of the neoadjuvant treatment: defined as no residual cancer cells in the resected specimen after curative resection
4. Patient's tolerability and completion rate of the neoadjuvant therapy

4. Study Design

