4.1 Overall Design

This phase II single-arm study is aimed to recruit 72 mid-to-low locally advanced rectal cancer patients who need neoadjuvant chemotherapy and radiotherapy. The pre-operative evaluation, including completed colonoscopy, neck-to-abdomen computed tomography, pelvis *magnetic resonance imaging*, and serum carcinoembryonic antigen, are arranged as a current practice guideline. After the patients agree to participate, a daily dose of 3g of BCM-95® curcumin is given as the chemotherapy starts. The curcumin therapy is continued during the whole neoadjuvant chemotherapy and radiation therapy. A complete blood count is checked during each cycle of chemotherapy.

Moreover, additional biochemical examinations with liver and renal function and adverse events (CTCAE version 5) and the criteria of the Radiation Therapy Oncology Group (RTOG) and European Organisation for Research and Treatment of Cancer (EORTC) are examined every 3 cycles of chemotherapy. The curcumin treatment is ended along with the completion of chemotherapy. An additional colonoscopy will be arranged 2 to 3 weeks after the radiation therapy completed to evaluate acute proctitis by Vienna Rectoscopy Score. After completion of the chemoradiation, colonoscopy and pelvis magnetic resonance imaging are conducted to evaluate the tumor response. Based on each surgeon's clinical judgment, the patient receives either curative surgery or a watch-and-wait strategy.

Run-in Cohort (n=6) Design

Study Design

This trial will begin with a run-in cohort of 6 patients receiving high-bioavailability curcumin (BCM-95) in combination with standard neoadjuvant chemoradiotherapy (nCRT) for mid-low-rectal cancer. The purpose of the run-in phase is to confirm safety, tolerability, and feasibility prior to expanding enrollment to the full Phase II cohort.

Objectives

- Primary Objective (Run-in cohort):
To evaluate the incidence of dose-limiting toxicities (DLTs), particularly hepatotoxicity and gastrointestinal adverse events (AEs), during curcumin administration with concurrent chemoradiotherapy.
- Secondary Objectives:
 - To confirm feasibility of oral curcumin administration and patient adherence.
 - To monitor preliminary gastrointestinal protective effects (e.g., radiation proctitis, diarrhea).
 - To validate safety monitoring and study logistics prior to full expansion.

Patient Population

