11.2.1 Efficacy analysis

Adverse events are assessed by the clinician on each cycle of admission, and additional record of adverse events (CTCAE version 5) by our research nurse on every 3 cycles of chemotherapy.

Clinical complete remission is evaluated on each colonoscopy examination after the neoadjuvant chemotherapy and radiation therapy completed according to Response Evaluation Criteria in Solid Tumors Version 1.1 (RECIST v1.1). In addition, the pathologist evaluates pathological complete response and tumor regression grade after curative resection.

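### The combined pathological-or-clinical complete response endpoint is defined only by the resected specimen, so patients on watch-and-wait cannot meet it as written

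*Protocol*

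**What the plan says.** The endpoint is item 4 of the secondary endpoints in the synopsis, item 3 of Section 3.2.2 and item 4 of Section 7. Its name is "Pathological or clinical complete response rate of the primary tumor after completion of the neoadjuvant treatment". The definition that follows is the same each time: "defined as no residual cancer cells in the resected specimen after curative resection".

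Section 4.1 and the synopsis (Study Procedures) put colonoscopy and pelvic MRI after chemoradiation to assess tumour response, and then state: "Based on each surgeon's clinical judgment, the patient receives either curative surgery or a watch-and-wait strategy". The schedule in Section 4.3 also carries a surgery or watch-and-wait column.

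Clinical complete response is a separate secondary endpoint, judged by RECIST v1.1, in the item just before this one. Section 11.2.1 describes the two assessments one after the other: "Clinical complete remission is evaluated on each colonoscopy examination after the neoadjuvant chemotherapy and radiation therapy completed", and "the pathologist evaluates pathological complete response and tumor regression grade after curative resection". It does not combine them and gives no denominator.

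**The concern.** The name promises a combined measure, but the definition supplies only the pathological half. A watch-and-wait patient has no resected specimen. Applied to the letter, the definition either counts that patient as a non-responder or drops the patient from the denominator. The second is possible because the synopsis prescribes listwise deletion and Section 11.2.5.1 excludes incomplete clinical data.

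The resulting rate then depends partly on how often watch-and-wait is chosen, and not only on tumour response. Section 3.1.2 makes the anti-neoplastic effect the secondary objective, and the synopsis opens by naming an improved pathological complete response rate among its aims. Section 11.2.5 compares this single arm with other trials and with the centre's retrospective data. If the use of watch-and-wait differs between those sources and this trial, the literal rate can differ for that reason alone. Leaving the reading open until the data are seen would also allow a choice between several rates.

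**Working it through.** The protocol states no rate, power or sample size for this endpoint, so there is no figure to reproduce. The check compares the texts and then illustrates the effect.

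**Texts side by side**

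- Name: pathological or clinical. Definition: pathological only, and it requires resection (synopsis, Section 3.2.2, Section 7).
- Pathway: surgery or watch-and-wait (synopsis, Section 4.1, Section 4.3).
- Section 11.2.1: clinical and pathological response are described separately and not joined.

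Three different rates are compatible with this wording: the literal definition over all patients, the literal definition over resected patients, and an unrestricted either-one rule. The last would also count a patient judged clinically complete whose specimen then shows residual cancer.

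**Illustration.** All inputs here are assumptions; the protocol gives none of them.

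- R = true combined complete response rate (pathological if resected, clinical if on watch-and-wait)
- w = share of complete responders on watch-and-wait
- u = share of non-responders on watch-and-wait

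Literal rate over all patients = R(1 − w).

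Literal rate over resected patients = R(1 − w) / [R(1 − w) + (1 − R)(1 − u)].

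With R = 30% and u = 0:

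| w | Over all patients | Over resected patients |
|---|---|---|
| 0% | 30.0% | 30.0% |
| 25% | 0.30 × 0.75 = 22.5% | 0.225 / (0.225 + 0.70) = 24.3% |
| 50% | 0.30 × 0.50 = 15.0% | 0.150 / (0.150 + 0.70) = 17.6% |
| 75% | 0.30 × 0.25 = 7.5% | 0.075 / (0.075 + 0.70) = 9.7% |

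Over all patients, for w from 25% to 75%, R = 20% gives 15.0% to 5.0% and R = 40% gives 30.0% to 10.0%.

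**Direction.** R(1 − w) never exceeds R, so over all patients the literal rate can only equal or understate the combined rate. Over resected patients the direction depends on who goes to watch-and-wait. With R = 30%:

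- w = 50%, u = 25%: 0.150 / (0.150 + 0.525) = 22.2%, below R
- w = 50%, u = 50%: 0.150 / (0.150 + 0.350) = 30.0%, equal to R
- w = 25%, u = 50%: 0.225 / (0.225 + 0.350) = 39.1%, above R

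**The case against.** The strongest reply is that the specimen clause defines only the pathological half, and that the item just before it, clinical complete response by RECIST v1.1, supplies the other half. Section 11.2.1 describes both assessments in turn, which suits that reading, and watch-and-wait responders would then count. This may well be the intent. But no section says so, and the clause is worded as the definition of the whole endpoint. The reading also leaves open what happens when clinical and pathological findings disagree in a resected patient.

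A second reply is that the denominator is commonly left to a statistical analysis plan, which may exist. That is fair for the denominator alone. The mismatch between name and definition is in the protocol itself.

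A reader might also infer more than the text supports:

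- *The rate is biased downward whatever the denominator.* This is certain only for the literal reading over all patients when some complete responders are on watch-and-wait. Over resected patients it depends on selection, which the protocol leaves to the surgeon without a response criterion.
- *Watch-and-wait responders are lost to the trial.* They are not, because the separate clinical endpoint needs no specimen.
- *This is the trial's main measure of anti-tumour effect.* Section 3.2.2 lists two response endpoints without ranking them.
- *The result cannot be compared with other series.* The protocol does not say how those series define response. If they report pathological response in resected patients, the literal definition over resected patients could match them.

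**Conclusion.** The point holds as an internal contradiction in a secondary endpoint: the name includes clinical response, the definition excludes it, and a pathway that the protocol allows produces patients who can never meet the definition. This is an error in the wording, and more than missing detail.

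The effect is nil if no complete responder is on watch-and-wait. With a true combined rate of 30%, 25% to 75% of complete responders on watch-and-wait and all non-responders resected, the shortfall is 7.5 to 22.5 percentage points over all patients (30 − 22.5; 30 − 7.5). Over resected patients it is 5.7 to 20.3 points (30 − 24.3; 30 − 9.7). These sizes rest wholly on the assumed inputs. The downward direction over resected patients also rests on complete responders going to watch-and-wait more often than others. That is plausible because the choice follows the response assessment, but it is not stated. The sample size is unaffected, since it is based on acute radiation proctitis (30% to 15%). The definition should be corrected before data accrue.

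**What to change.** Use one identical definition in the synopsis, Section 3.2.2 and Section 7:

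- **Resected patients:** pathological complete response, that is, no residual cancer cells in the specimen. Pathology decides, whatever the earlier clinical finding.
- **Watch-and-wait patients:** clinical complete response, by the same criterion as the separate clinical response endpoint, at the post-treatment response assessment already planned.
- **Denominator:** all treated patients.

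Report pathological complete response among resected patients separately, with the number on watch-and-wait beside it, for comparison with external series.

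The sentence should name the assessment time. As the schedule in Section 4.3 reads here, the last colonoscopy is in the week 19 column and the MRI in the weeks 22–24 column, so the post-treatment assessment may not be a single visit (the table may have been distorted in extraction).

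The cost is a wording amendment in three places. Both assessments are already planned, and no procedure, visit or patient is added.

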4.1 Overall Design

This phase II single-arm study is aimed to recruit 72 mid-to-low locally advanced rectal cancer patients who need neoadjuvant chemotherapy and radiotherapy. The pre-operative evaluation, including completed colonoscopy, neck-to-abdomen computed tomography, pelvis *magnetic resonance imaging*, and serum carcinoembryonic antigen, are arranged as a current practice guideline. After the patients agree to participate, a daily dose of 3g of BCM-95® curcumin is given as the chemotherapy starts. The curcumin therapy is continued during the whole neoadjuvant chemotherapy and radiation therapy. A complete blood count is checked during each cycle of chemotherapy.

Moreover, additional biochemical examinations with liver and renal function and adverse events (CTCAE version 5) and the criteria of the Radiation Therapy Oncology Group (RTOG) and European Organisation for Research and Treatment of Cancer (EORTC) are examined every 3 cycles of chemotherapy. The curcumin treatment is ended along with the completion of chemotherapy. An additional colonoscopy will be arranged 2 to 3 weeks after the radiation therapy completed to evaluate acute proctitis by Vienna Rectoscopy Score. After completion of the chemoradiation, colonoscopy and pelvis magnetic resonance imaging are conducted to evaluate the tumor response. Based on each surgeon's clinical judgment, the patient receives either curative surgery or a watch-and-wait strategy.

Run-in Cohort (n=6) Design

Study Design

This trial will begin with a run-in cohort of 6 patients receiving high-bioavailability curcumin (BCM-95) in combination with standard neoadjuvant chemoradiotherapy (nCRT) for mid-low-rectal cancer. The purpose of the run-in phase is to confirm safety, tolerability, and feasibility prior to expanding enrollment to the full Phase II cohort.

Objectives

- Primary Objective (Run-in cohort):
To evaluate the incidence of dose-limiting toxicities (DLTs), particularly hepatotoxicity and gastrointestinal adverse events (AEs), during curcumin administration with concurrent chemoradiotherapy.
- Secondary Objectives:
 - To confirm feasibility of oral curcumin administration and patient adherence.
 - To monitor preliminary gastrointestinal protective effects (e.g., radiation proctitis, diarrhea).
 - To validate safety monitoring and study logistics prior to full expansion.

Patient Population

- 6 patients with stage II–III mid-/low-rectal adenocarcinoma scheduled for standard nCRT will be enrolled.
- Patients must meet all eligibility criteria, including adequate hematologic and hepatic function.

Treatment

- Investigational Product: BCM-95 curcumin, administered orally throughout the course of nCRT.
- Concomitant Therapy: Standard long-course pelvic radiotherapy (50.4 Gy/28 fractions) plus concurrent capecitabine.

Safety Monitoring

- DLT Evaluation Window: Entire course of concurrent nCRT (6 weeks).
- DLT Criteria (adapted for this study):
 - Grade ≥3 non-hematologic toxicity (CTCAE v5.0), excluding expected alopecia and transient nausea/vomiting.
 - ALT or AST >3× ULN confirmed on repeat test, or ALT/AST >5× ULN at any time.
 - Total bilirubin >2× ULN with concurrent ALT/AST elevation.
 - Grade 4 hematologic toxicity lasting >7 days.
 - Any toxicity requiring treatment interruption >2 weeks.
- Monitoring Plan:
 - CBC, renal, and liver function tests weekly during nCRT.
 - Symptom assessment (diarrhea, proctitis, fatigue) using CTCAE v5.0 and RTOG scoring.

[figure not shown]
Decision Rules

- If ≤1 of 6 patients develops a DLT, the study will proceed to Phase II enrollment (planned n=72).
- If ≥2 of 6 patients develop a DLT, the Principal Investigator (PI) and Co-Principal Investigator (Co-PI) will review safety data, and dose adjustment, protocol amendment, or early termination will be considered before further enrollment.

Transition to Full Cohort

- Upon the confirmation of safety and IRB notification, the trial will expand to the Phase II cohort.
- The same treatment regimen will be maintained unless other safety issues come into concern.

Flow Chart (試驗流程圖) :

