1.3 UFUR (one cycle)

*Tegafur 300-350 mg/m²/day and leucovorin 90mg/day PO on day 1 to day 5, then rest for 2 days for 2 weeks

1.4 The radiation therapy modules are as follows:

Short-Course (hypofractionated, 25 Gy/5 fractions) Radiotherapy (SCRT)

2. Prohibited Therapy : cell therapy, immunotherapy

Statistical Methods :

1. Main study Hypothesis : Equality Superiority Non-inferiority
 Equivalence Other

2. Estimated Sample Size : 整個試驗預計納入人數_72_，整個試驗可評估人數_64_
 本中心預計納入人數_72_，本中心可評估人數_64_

3. Efficacy assessment group : Intent-to-treat (ITT) Per-Protocol (PP)
 Other _____

附註：意圖治療：Intent-to-treat (ITT)；依計畫書：Per-Protocol (PP)

4. Interim analysis : Yes No

5. Statistical methods : descriptive statistics, Kaplan-Meier method, T-test

6. Handling of Missing Data : Listwise deletion

2. Introduction and Rationale

The primary treatment method for non-metastatic locally advanced rectal cancer is TME (Total mesorectal excision). In recent years, neoadjuvant chemotherapy and radiation therapy have been proven to decrease local recurrence and increase the possibility of organ preservation. [5, 6] However, radiation proctitis is a joint adverse event in one-third of patients one week after radiation treatment is complete; [7] and severe acute toxicity was observed in 4.2% of patients. [8]

Curcumin (diferuloylmethane) is a hydrophobic polyphenol derived from the rhizome of *Curcuma longa*. It has been proven an anti-inflammatory agent as an NF- κ B inhibitor [9] and has numerous intrinsic and extrinsic anti-neoplastic pathways. [10] The murine model showed that oral curcumin could alleviate irinotecan-induced intestinal injury via attenuation of NF- κ B activation, oxidative stress and endoplasmic reticulum stress. [11] One phase I clinical trial showed the oral form curcumin can be safe even up to 8 gram per day. [12] Moreover, the USFDA has designated oral curcumin as a “generally recognized as safe” agent. (US FDA; per 21 CFR 182.10, 182.20) However, due to its hydrophobic feature, poor bioavailability limited its clinical application. [13]

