4.2 Number of Patients

Sample size calculation is performed using one proportion equality test using the exact test to achieving an 80% power at the 5% level of significance. With the expectation of an -15% of improvement of acute radiation proctitis (30% to 15%), the total estimated patients number in a single-arm trial required is 64. Consider the patient with incomplete data and drop-out rate of 10%, the total estimated number of sample size is 72. Sample size calculation was performed using PASS software (Power Analysis and Sample Size version 2021, NCSS, Kaysville, Utah, USA).

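### The protocol does not settle whether the six run-in patients are inside the 72, or whether they enter the primary test

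*Protocol*

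**What the plan says.** **Totals.** The synopsis, Statistical Methods item 2, states "整個試驗預計納入人數_72_，整個試驗可評估人數_64", that is, 72 expected to be enrolled and 64 evaluable across the whole trial. Section 4.2 ends its calculation with "the total estimated number of sample size is 72", and Section 11.1 repeats it. Section 4.1 opens with "This phase II single-arm study is aimed to recruit 72 mid-to-low locally advanced rectal cancer patients". The sample size text never mentions a run-in.

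**Run-in.** Later in Section 4.1: "This trial will begin with a run-in cohort of 6 patients", whose purpose is to confirm safety "prior to expanding enrollment to the full Phase II cohort". The Decision Rules continue: "If ≤1 of 6 patients develops a DLT, the study will proceed to Phase II enrollment (planned n=72". With two or more DLTs, the investigators review the data and consider dose adjustment, amendment or termination.

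**Overlap with the primary endpoint.** The DLT list in Section 4.1 includes grade 3 or higher non-haematologic toxicity, with narrow exclusions. The primary endpoint in Section 3.2.1 is grade 3 enteritis/proctitis.

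**Regimen.** The Treatment paragraph of the run-in gives long-course radiotherapy (50.4 Gy in 28 fractions) with capecitabine. The synopsis, the schedule in Section 4.3, and Sections 6.1 and 6.2 describe short-course radiotherapy (25 Gy in 5 fractions in the synopsis and 6.2), and capecitabine is not among the chemotherapy options of 6.2. The paragraph on transition to the full cohort nevertheless says that the regimen will stay the same.

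The protocol does not say whether the six count towards 72 or 64, or whether they are in the primary analysis.

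**The concern.** The protocol itself commits to 72 and 64, and what those numbers mean depends on where the six belong. If they are extra, the whole-trial total in the synopsis is wrong by six. If they are inside the 72 and set aside, the evaluable number behind the power statement is not reached. If they are inside and counted, one radiation-proctitis rate, tested against a single 30% reference, mixes patients described under two radiotherapy regimens. Six of those patients would also have been let through by a gate that counts the primary event against them. That selection pushes the observed rate down, which is the direction of a curcumin benefit.

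**Working it through.** **Inputs.** Reference rate 30%, target 15%, exact one-proportion test, 80% power, 5% level, 64 evaluable, 10% loss, 72 enrolled (Sections 4.2 and 11.1). Two-sided testing (Section 11.2). Run-in of 6, gate passed with 0 or 1 DLT (Section 4.1).

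**1. The plan's own figures.** Two-sided normal approximation:
n = [(1.960·√(0.30·0.70) + 0.842·√(0.15·0.85)) / 0.15]² = 63.86, rounded up to 64.
Inflation: 64 / 0.9 = 71.1, rounded up to 72.
Both figures reproduce. The exact test that the text names gives 75.4% power at n = 64 (reject at 11 or fewer events, lower tail 0.0145), so the 80% belongs to the approximation. That shortfall exists whatever happens to the run-in.

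**2. Four readings, at 10% loss.**

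| Reading | Enrolled | Evaluable for primary test | Consequence |
|---|---|---|---|
| Six inside 72, counted | 72 | 72 × 0.9 = 64.8 | 64 met; run-in patients pooled |
| Six inside 72, not counted | 72 | 66 × 0.9 = 59.4 | about 5 short of 64 |
| Six outside 72, not counted | 78 | 72 × 0.9 = 64.8 | 64 met; synopsis total wrong |
| Six outside 72, counted | 78 | 78 × 0.9 = 70.2 | synopsis total wrong; run-in patients pooled |

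**3. Power at 59.**
Normal approximation: Φ[(0.15·√59 − 1.960·√0.21) / √0.1275] = Φ(0.71) = about 76%. The same formula at 64 gives Φ(0.85) = about 80%.
Exact: reject at 10 or fewer of 59 (lower tail 0.0167), power 73.5% against 75.4% at 64.

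**4. Size of the gate effect if the six are pooled into 64.** Assumptions: proctitis is the only DLT, every primary event in the six counts as a DLT, both groups share one true rate, events are independent, and the gate has been passed.

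- True rate 30%: P(0 or 1 of 6) = 0.1176 + 0.3025 = 0.420. Expected events in the six given a pass: 0.3025 / 0.4202 = 0.72, against 6 × 0.30 = 1.80. Expected pooled rate: (0.72 + 58 × 0.30) / 64 = 28.3%, a shift of 1.7 points.
- True rate 15%: P(pass) = 0.776, expected events 0.51 against 0.90, pooled rate (0.51 + 58 × 0.15) / 64 = 14.4%, a shift of 0.6 points.
- With other DLTs at an assumed rate of up to 20% (not in the protocol), the shifts reach 1.9 and 0.9 points.

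**5. False-positive probability at a true 30%, n = 64.**

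| Cut | No gate | Among trials that pass | Over all trials, stopping if the gate fails |
|---|---|---|---|
| 11 or fewer (two-sided 5%) | 1.45% | 2.61% | 2.61% × 0.420 = 1.09% |
| 12 or fewer (one-sided 5%) | 2.99% | 5.12% | 5.12% × 0.420 = 2.15% |

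If failed trials simply carried on unchanged, the overall figure would return to the no-gate column. Either way it is not inflated.

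**The case against.** The best defence is that the protocol states no second total. Every explicit total is 72, the figure 78 appears nowhere, and the language of expanding to the full cohort fits growth from 6 to 72. The planned n in the Decision Rules may be the same 72. The protocol is silent on pooling, and the make-up of the analysis set is often left to a statistical analysis plan, which was not available here. Two or more DLTs lead to review, not to a certain stop. The DLT window is the 6-week chemoradiotherapy course, while proctitis is assessed about 2 weeks (Section 3.2.1) or 2 to 4 weeks (Section 7) after radiotherapy, so some primary events may fall outside the gate.

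Much of this stands. A reader might infer that the protocol commits to 78, that it fails to deliver 64 evaluable patients, or that its primary rate is materially biased by the gate. The documents support none of these. The total of 78 is only the more natural of two readings, 64 is missed under one reading of four, and the gate figures are small and assume complete overlap.

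The ambiguity itself remains. The protocol fixes 72 and 64 without saying where the six belong, and each reading leaves something to correct. The defence also does not reach the regimen conflict, which is a stronger obstacle to pooling than the gate.

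**Conclusion.** The concern holds as an unresolved ambiguity of moderate importance. The total is 72 or 78, and the place of the six in the primary test is open. The numerical stakes are limited: at worst about 59 evaluable in place of 64, costing about 2 points of exact power or about 4 points by the normal approximation. A pooled rate would read about 1.7 points low at a true 30% and 0.6 points low at 15%. These shifts are upper bounds under complete overlap of proctitis with the DLT definition and window, with proctitis the only DLT and one common event rate.

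The gate figures say nothing about the effect of mixing two radiotherapy regimens. The protocol gives no regimen-specific rates from which to calculate that effect, so it cannot be sized here. It is still the main reason why the denominator has to be settled before enrolment.

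**What to change.** 1. State in Sections 4.1 and 11 that the six run-in patients are analysed for DLTs and safety and are not part of the primary one-proportion test. A pooled result may be shown as a sensitivity analysis only.
2. Make the synopsis and Sections 4.1, 4.2 and 11.1 agree on one of two versions: 78 in total, with 72 in Phase II and 64 evaluable; or 72 in total, with about 59 evaluable and the power restated for that number.
3. Reconcile the radiotherapy and chemotherapy described for the run-in in Section 4.1 with the synopsis and Sections 4.3, 6.1 and 6.2, and with the statement that the regimen is unchanged on expansion. Which regimen applies is for the investigators to settle.

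The cost is a few sentences, plus either a stated total that is larger by six or an evaluable number that is lower by about five.
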